#### **4.1 Analysis Population**

The analyses will be based on a Safety Population, which includes randomized subjects who receive at least one dose of study treatment and which classifies subjects by the more frequently received drug.

#### **4.2 Global Study Completion Date**

The sponsor will notify the sites approximately three months prior to the global study completion date (GSCD) for each study so that they can schedule visits with all subjects who are alive and have not withdrawn consent. At that visit the investigators should try to assess whether the subjects have had any MACE, Hospitalized for HF or Thromboembolic event. At a minimum the investigators will attempt to contact each subject to determine whether that subject is still alive. Additionally, investigators will request that subjects who continued study treatment until this visit come in for another follow-up visit four weeks later.

Operationally this plan is designed to capture all MACE, hospitalized for HF and Thromboembolic events that occurred in subjects still being followed and with onset within three

months of GSCD in the clinical database. Should subjects who remained on study treatment until that visit subsequently experience MACE, Thromboembolic events or hospitalized for HF between that visit and four weeks later, these events may also be captured.

Analytically, any outcome event with onset on or before the last contact date will be included in the primary safety outcome analysis, and all subjects without events will be censored at the last contact date.

The earliest GSCD of a pair of studies will be a date that ensures each pair of studies will have the planned number of safety outcome events (i.e., 631) and each study in each pair has the protocol-required amount of safety follow-up.

### **4.3 Reference dates**

This SAP uses the following terms to refer to dates used to calculate time.

Date of last visit for MACE and other adjudicated events is the date of the last visit when all events could be assessed. This visit may be conducted in person at the site or by telephone.

Date of last contact is the last date when the site had any contact at all with the subject.

### **4.4 Primary MACE Analysis**

The endpoint for the primary analysis is defined as the first occurrence of all-cause mortality, adjudicated nonfatal MI, or adjudicated nonfatal stroke after taking the first dose of investigational drug. Treatment comparisons will be based on the estimated hazard ratio and its 95% CI from the Cox model described below. As specified earlier, there will be a primary MACE analysis for each pair of trials, one for the CI-0014 and CI-0015 NDD-CKD trials and one for the CI-0016 and CI-0017 DD-CKD trials.

Counts and proportions of patients who experience a primary endpoint event will be calculated for each treatment arm, as well as the proportion difference (95% CI) in proportions between the groups. Mantel-Haenszel confidence interval will be reported for the proportion difference. In addition to event rate, person-years of follow-up for the primary endpoint and the incidence rate, calculated by dividing the number of patients who developed the event during the study period by the event-specific person-years of at-risk follow-up, will be provided.

For each subject who has experienced a MACE, the time to the first adjudicated MACE is defined as the date of the first MACE – date of first dose +1.

Subjects who have not experienced a MACE will be censored at the date of the last study contact (visit or telephone contact) at which all components of MACE were assessed.

For each of the four studies and for each pair of studies, Kaplan-Meier curves for the time to first adjudicated MACE will be generated.

For each pair of studies, analysis of time to first MACE will be based on a stratified Cox regression model with study as a stratification factor. The model will also include covariates of baseline Hb, randomization strata of region (US; EU; ROW) and NYHA (0 or I; II or III), sex (male; female), age ( $> 65$ ;  $\leq 65$ ), race (white or non-white), preexisting cardiovascular disease as defined in Section 5.1 (yes/no), and diabetes mellitus (yes/no). The following kernel of SAS code (details in Appendix A) will be used for PRO2TECT (for INNO2VATE, the study strata will be replaced with CI-0016/17):

```
proc phreg;
  strata /*study pair*/ CI-0014/15;
  model time to first MACE * censor = trtgrp
    /*covariates*/ age sex race pre-existing
    cardiovascular disease DM region NYHA
    Hb_base;
run;
```

The hazard ratio (vadadustat/darbepoetin alfa) and its 95% confidence interval will be presented for each study and each pair of studies. For a given pair of studies (PRO2TECT and INNO2VATE), Vadadustat will be considered to have non-inferior risk of MACE relative to darbepoetin alfa if the upper limit of this 95% CI of the pair is less than 1.25 (for FDA assessment) or 1.30 (for EMA assessment).

Vadadustat will be considered superior to darbepoetin alfa with respect to the MACE outcome in a particular disease population if the upper limit of this 95% CI of the pair of studies is less than 1.

The stratified Cox regression model (primary safety analysis) allows the underlying hazard to vary by stratum (i.e. by study) but it makes the assumption that the effects of covariates are proportional over time within each stratum. The proportionality assumption will be assessed graphically and visually. If the assumption is violated, alternative method may be explored.

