8.4.4 Dosing and Dose Adjustment Guidelines

Dosing will be initiated at the Baseline visit, and the first dose of study medication (vadadustat or darbepoetin alfa) will be administered at the investigative site after other Baseline visit procedures have been completed. The investigator may elect to postpone the initial dose of study medication until a subsequent visit based on the subject's Hb level or Hb trajectory assessed at the Baseline visit, or based on timing of last ESA dose given during Screening.

For all subjects, it is recommended that no additional ESA doses be administered after SV2 and prior to the Randomization visit.

Year 1-4 Treatment Period Visits

Hemoglobin will be monitored via HemoCue throughout the study to determine if the dose of study medication (vadadustat or darbepoetin alfa) will be adjusted, interrupted, or maintained. From Weeks 0 to 12, Hb will be obtained via HemoCue every 2 weeks for monitoring for dose adjustment. From Week 12 to Week 52, Hb will be monitored every 4 weeks via HemoCue.

From Week 53 through the study end, Hb will continue to be monitored via HemoCue to determine if the dose of study medication will be adjusted, interrupted, or maintained. Any unscheduled measurement taken between study visits will be recorded in the appropriate CRF and the subject's source when a Hemocue is taken. Hemoglobin will also be assessed with a CBC through the central laboratory for efficacy and safety evaluations; however, dose adjustments should be based on the HemoCue Hb value. If the Investigator has an immediate clinical concern about a subject's HemoCue value, the Investigator may use clinical judgment and repeat the HemoCue Hb, use local lab values, or wait for central lab results. The test method utilized to inform your treatment decision must be recorded in the appropriate CRF and subject's source.

Year 2-4 Monthly Hb Monitoring

Additionally, after Week 52, the Hb drawn as part of the local standard of care labs must be monitored monthly for dosing oversight. Per the Dosing Algorithms, if the Hb value suggests a dose adjustment is needed, an unscheduled visit must be performed.

If monthly standard of care labs are not available, a study unscheduled visit must be performed. This visit will include, at minimum, the Hb measurement via HemoCue, dose adjustment assessment, and adverse events assessment.

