11.2 Study Analysis Populations

The following analysis populations will be used in this study:

- Randomized population: defined as all randomized subjects
- Full analysis population: defined as randomized subjects receiving 1 or more doses of study medication and had at least one Hb assessment during the primary efficacy evaluation period. This population will be analyzed based upon the randomized treatment.
- Per protocol (PP) population: defined as all randomized subjects who received study medication (vadadustat or darbepoetin alfa) during the primary evaluation period, had at least 2 Hb assessments during the primary evaluation period, received no rescue therapy (with ESA or RBC transfusion) in the 8 weeks prior to the evaluation period, and have no protocol deviations affecting the primary endpoint analyses. Protocol deviations leading to exclusion from the per protocol population will be specified prior to database lock on a blinded basis and recorded in a separate document.
- Safety population: defined as all subjects who received at least 1 dose of study medication. This population will be analyzed based upon the actual treatment received.

Efficacy analyses will utilize the randomized, full analysis, and PP populations while safety analyses (including MACE) will utilize the randomized population.

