11.7.1 Analysis of MACE and Expanded MACE Components

The primary safety endpoint, time to the first adjudicated MACE, will be analyzed as [date of the first MACE minus the date of randomization +1]. A MACE is defined as all-cause mortality, non-fatal myocardial infarction, or non-fatal stroke. Subjects who have not experienced a MACE by study closure will be censored on the date of their last study assessment. The hazard ratio (vadadustat/darbepoetin alfa) and its 95% confidence interval will be obtained from a stratified Cox proportional hazards model. As this study has not been designed to provide a stand-alone assessment of MACE, this analysis will be considered a descriptive analysis. A similar analysis as described for the primary analysis of the MACE endpoint will be performed with censoring of subjects 4 weeks following discontinuation of study medication if they did not have a MACE prior to that time.

An additional analysis as described for the primary analysis of the MACE endpoint will be performed with censoring at time of chronic dialysis initiation for subjects who have progressed to chronic dialysis and who did not have a MACE prior to that time.

The following safety endpoints will also be summarized using time to event methods as for MACE:

- 1) Individual components (all-cause mortality, non-fatal myocardial infarction, non-fatal stroke) of MACE
- 2) Thromboembolic events (defined as arterial thrombosis, DVT, PE, or vascular access thrombosis)
- 3) Hospitalization for heart failure

- 4) Expanded MACE, defined as all-cause mortality, non-fatal myocardial infarction, non-fatal stroke, hospitalization for HF, or thromboembolic event

For these endpoints the incidence ("yes"/"no") of the endpoint will be presented for each treatment arm. Kaplan-Meier curves will be presented for each endpoint as the time of endpoint free survival (ie, time until endpoint or death).

The primary MACE analysis will be based upon all events that accrue over the 2 NDD-CKD studies (Studies AKB-6548-CI-0014 and AKB-6548-CI-0015) (see [Section 11.1.2, Sample Size for the Primary Safety Endpoint](#)).

The SAP for this pooled MACE assessment in NDD-CKD subjects provides details of the primary analyses for MACE, for individual components of MACE, and for an expanded version of MACE. Details of sensitivity analyses and subgroup analyses are also provided in the MACE SAP.

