## 2.5 Sample Size

The primary safety endpoint is the time from first dose date to the first adjudicated MACE. This section describes the justification for the sample sizes of the four studies.

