### **C.1. Background**

Many scientific questions are unanswered to date and there remains an unmet medical need for a new therapy for anemia in CKD. Among the unanswered questions are:

- Can Hgb be safely raised with a novel agent other than an ESA without increasing CV risk?
- Are hypoxia-inducible factor prolyl-hydroxylase inhibitors (HIF-PHIs) as safe as or safer than ESAs?

The primary safety outcome in each study is MACE, defined as all-cause mortality, nonfatal myocardial infarction (MI) or nonfatal stroke, occurring at any time following randomization and prior to each subject's end-of-study date. The endpoint for the primary analysis will be the first occurrence after randomization of all-cause mortality, adjudicated nonfatal MI, or adjudicated nonfatal stroke. Treatment comparisons will be based on the estimated hazard ratio (vadadustat/darbepoetin alfa) and its 95% CI from a Cox proportional hazards model for the pair of NDD studies and for the pair of DD studies.

Vadadustat will be considered to have non-inferior risk of MACE relative to darbepoetin alfa if the upper limit of this 95% CI of each pair of studies is less than or equal to the prespecified noninferiority margin.

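### The SAPs start the primary MACE analysis at first dose in dosed subjects only, while the current protocol and the MACE SAP's own margin appendix count from randomization

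*SAP*

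**What the plan says.** MACE SAP 2.5 states: "The primary safety endpoint is the time from first dose date to the first adjudicated MACE". Sections 2.3, 3.2, 4, 4.4 and 4.6 use the same origin. Section 4.4 counts deaths and "adjudicated nonfatal MI, or adjudicated nonfatal stroke after taking the first dose of investigational drug". Section 4.1 sets the population as one that "includes randomized subjects who receive at least one dose of study treatment and which classifies subjects by the more frequently received drug". Main SAP 2.8 also starts at first dose, and main SAP 3.1 assigns MACE to the safety population.

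The current protocol (Amendment 7-COL) differs on both counts. Section 11.7.1 computes the time as "date of the first MACE minus the date of randomization +1", and 11.1.2 and the synopsis agree. Section 11.2 says that "safety analyses (including MACE) will utilize the randomized population", and the synopsis again agrees. Appendix section C.1 of the MACE SAP, which justifies the margin, describes the primary endpoint as "the first occurrence after randomization of all-cause mortality".

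Allocation is open-label and takes place at the Baseline visit. The default is to dose at that visit, but protocol 8.4.4 adds: "The investigator may elect to postpone the initial dose of study medication until a subsequent visit". The stated grounds are the Hb level or trajectory at Baseline and the timing of the last ESA dose.

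**The concern.** Under the SAP definition, a death, MI or stroke between allocation and first dose is not an event, and that interval is not time at risk. A subject who is randomized, learns the arm and never takes study drug leaves the MACE analysis altogether. Both exclusions depend on what happens after the site and the subject know the treatment. The arms could differ here: one starts a new tablet, while the other receives an injectable ESA that may be the subject's existing one. The grounds for postponing (Hb and recent ESA dosing) may also be prognostic.

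At stake is the confirmatory safety test. The hazard ratio is compared with 1.25 (FDA) and 1.30 (EMA), and any bias from these exclusions could run either way. The efficacy primary analysis does not have this weakness: main SAP 9.1.4 keeps subjects who never receive treatment.

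**Working it through.** **Definitions side by side**

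| Source | Time origin | Population |
|---|---|---|
| MACE SAP 2.3, 2.5, 3.2, 4, 4.1, 4.4, 4.6 | first dose | at least one dose |
| Main SAP 2.8, 3.1 | first dose | at least one dose |
| Current protocol synopsis, 11.1.2, 11.2, 11.7.1 | randomization | all randomized |
| MACE SAP appendix C.1 | randomization | not stated |

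**Is there a planned analysis that repairs this?** The time-to-event rows in MACE SAP 4.6 start at first dose. The restricted-mean analysis in section 6 changes the summary measure but not the population. Protocol 11.7.1 says that sensitivity analyses are in the MACE SAP, but none there uses all randomized subjects from randomization.

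**The plan's own figure.** Inputs from MACE SAP 2.5.1: margin 1.25, true HR 1.0, two-sided 95% CI, 80% power, 1:1 allocation. The Schoenfeld formula gives

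d = 4(1.960 + 0.842)² / (ln 1.25)² = 630.5, rounded up to 631.

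With 631 events, SE(log HR) = 2/√631 = 0.0796. Power is 80.0% (margin 1.25, HR 1.0), 90.9% (margin 1.30, HR 1.0) and 93.1% (margin 1.25, HR 0.95). All the stated figures reproduce. Because the trials run to an event count, changing the time origin and population leaves these values as they are. It changes which events make up the 631.

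**How many events could be excluded?** The documents give 3700 subjects in the pair, 10% MACE a year and about 2 years' mean follow-up. The never-dosed and delayed fractions below are assumptions.

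- *Never dosed.* Events = 3700 × f × (1 − 0.9²) = 3700 × f × 0.19. For f = 0.1%, 0.5%, 1% and 2% this is 0.7, 3.5, 7.0 and 14.1 events, both arms together.
- *Delayed start.* Events = 3700 × f × 0.10536 × weeks/52, where 0.10536 = −ln 0.9. For 5% delayed 2 weeks this is 0.7; for 10% delayed 4 weeks, 3.0; for 20% delayed 4 weeks, 6.0. An extreme corner of 25% delayed 8 weeks gives 15.0.
- The two ranges overlap, because a subject who dies before dosing is also never dosed.

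**What could that do to the result?** At HR 1.00 the upper limit is exp(1.96 × 0.0796) = 1.169. The largest HR that still passes is 1.25/1.169 = 1.069, which is about 326 versus 305 events. From that boundary, restoring k excluded events that all belonged to vadadustat moves the upper limit as follows:

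| k | Upper limit |
|---|---|
| 0 | 1.250 |
| 1 | 1.254 |
| 5 | 1.269 |
| 10 | 1.287 |

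Putting every excluded event in one arm is a worst case. With 7 excluded events split 60/40 (4.2 versus 2.8), the net difference is 1.4 events, or 1.4/315.5 ≈ 0.4% in the HR. Starting from HR 1.00, even 10 added vadadustat events give an upper limit of 1.204, still below 1.25.

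**The case against.** The strongest reply is precedence. Main SAP section 1 says the SAP governs where the protocol differs, both SAPs use first dose, and protocol 11.7.1 calls the single-study analysis descriptive and refers the pooled analysis to the MACE SAP. The current protocol text is also a Colombia-specific amendment of one of the four trials that the MACE SAP covers, and appendix C.1 is background to the margin. This largely settles which text operates. It does not settle whether the analysis is sound, and it leaves the MACE SAP inconsistent with itself.

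A second reply concerns direction. Adding never-dosed subjects and pre-dose time can pull the HR toward 1, which helps a noninferiority claim. That stands, and it is the reason to keep the dosed-population result beside the randomized one.

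A reader might draw three stronger conclusions that the documents do not support:

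- *That the loss is invisible.* Main SAP 4.3 already tabulates subjects randomized but not treated, by arm. What is missing is the delay to first dose and the MACE in that gap.
- *That postponement is an open option.* No maximum delay is given, but the grounds are stated, dosing at Baseline is the default, and visits are every 2 weeks to Week 12.
- *That power falls to about 68%.* That figure needs a true 3% upward shift in the HR, roughly a net loss of 10 events from one arm. The assumed ranges give fewer than 10 events in both arms together over much of their span, and nothing in the documents shows a difference between arms.

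**Conclusion.** The point holds as a flaw in definition. The primary MACE comparison starts at a post-allocation time, in a subset formed after allocation, in an open-label trial, and no planned MACE analysis uses all randomized subjects from randomization. The SAPs conflict with the current protocol, and the MACE SAP conflicts with its own margin appendix.

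The size is unknown and probably small: on the assumed ranges, roughly 1 to 14 never-dosed MACE across both arms plus a few pre-dose events, with the direction of any bias unknown. It would matter only if the result fell close to the margin or the exclusions were strongly one-sided. The case for changing it rests on principle and low cost, not on a demonstrated distortion.

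**What to change.** Before database lock and unblinding:

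- In MACE SAP 2.3, 2.5, 3.2, 4, 4.1, 4.4 and 4.6 and main SAP 2.8 and 3.1, define the primary MACE analysis on all randomized subjects by assigned arm, with time = date of first MACE − date of randomization + 1. This matches the current protocol and appendix C.1. Section 4 of the MACE SAP already names the randomized assignment as the predictor.
- Use the same definition to count the 631 events, so that the stopping trigger and the analysis refer to the same events.
- Keep the first-dose, dosed-population analysis as supportive.
- Add by-arm tables of days from randomization to first dose and of MACE before first dose.

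The cost is SAP wording, programming and two tables, plus a check of the wording against the other three protocols, which are not among these documents. For this study the data are already planned: AEs are collected from randomization (protocol 10.3.1), MACE is asked about at each post-randomization visit (9.2.1), and vital status is sought for every randomized subject (7.5.5.5). Event target and power are unaffected.

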## 2.8 Safety

The primary safety endpoint is the time from the first dose date to the first adjudicated MACE (defined as all-cause mortality, nonfatal myocardial infarction, or nonfatal stroke).

The primary safety analysis will include all first events that accrue over the pair of PRO2TECT studies. The sample size for the MACE endpoint is based on a 2-sided 95% confidence interval for the hazard ratio (HR) (vadadustat/darbepoetin alfa) and a noninferiority margin of 1.25 (upper bound of the 95% confidence interval) for FDA decision making. Under the assumption that the MACE rate is the same in the 2 groups (i.e., the HR =1), 631 subjects with MACEs will be required in the 2 trials combined to have 80% power to establish noninferiority. If the HR is 0.95 favoring vadadustat, the power will be above 90%. Based on a noninferiority margin of 1.30 for EMA decision making, the power will be above 90% under the assumption that the HR is 1.

Additional safety presentations are described below ([Section 7](#) and [Section 10](#)).

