A by-subject listing of all TEAEs will be provided. This listing will be presented by treatment group and will include: center, subject identifier, age, sex, race, AE (SOC, PT, and verbatim term), study day of onset, study day of resolution, duration, severity, seriousness, relationship to the study medication, action taken, outcome and causality.

AESI, listed in [Appendix F](#), will be summarized by treatment group. The number and percentage of subjects reporting these AESI will be provided.

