**Table B 1. Outcome Variables and Covariates in the Multiple Imputation Models**

| Type       | Variable a | Description  | Baseline, Post, Outcome | Levels |
|------------|-----------------------|--|-------------------------|--------|
| Continuous | HBBL                  | Baseline Hb  | Baseline                | n/a    |
| Continuous | HBS1                  | Hb in Weeks 2-8  | Post                    | n/a    |
| Continuous | HBS2                  | Hb in Weeks 10-20  | Post                    | n/a    |
| Continuous | HBS3                  | Hb in PEP (Weeks 24-36)  | HBCHGS3, HBRNGS3        | n/a    |
| Continuous | HBS4                  | Hb in SEP (Weeks 40-52)  | HBCHGS4, HBRNGS4        | n/a    |
| Continuous | TIBCBL                | Baseline TIBC  | Baseline                | n/a    |
| Continuous | HEPCNBL               | Baseline hepcidin  | Baseline                | n/a    |
| Continuous | FERRBL                | Baseline ferritin  | Baseline                | n/a    |
| Continuous | UACRBL                | Baseline uACR (PRO2 only)  | Baseline                | n/a    |
| Continuous | CRPBL                 | Baseline CRP   | Baseline                | n/a    |
| Continuous | TSATBL                | Baseline TSAT  | Baseline                | n/a    |
| Continuous | EGFRBL                | Baseline eGFR (PRO2 only)  | Baseline                | n/a    |
| Continuous | TIBCS3                | TIBC in PEP (Weeks 24-36)  | Post                    | n/a    |
| Continuous | HEPCNS3               | Hepcidin in PEP (Weeks 24-36)  | Post                    | n/a    |
| Continuous | FERRS3                | Ferritin in PEP (Weeks 24-36)  | Post                    | n/a    |
| Continuous | UACRS3                | uACR in PEP (Weeks 24-36) (PRO2 only)  | Post                    | n/a    |
| Continuous | CRPS3                 | CRP in PEP (Weeks 24-36)   | Post                    | n/a    |
| Continuous | TSATS3                | TSAT in PEP (Weeks 24-36)  | Post                    | n/a    |
| Continuous | EGFRS3                | eGFR in PEP (Weeks 24-36) (PRO2 only)  | Post                    | n/a    |
| Continuous | ESABL                 | Baseline ESA dose  | Baseline                | n/a    |
| Continuous | TDIALBL               | Time on dialysis prior to Screening Visit 1 (INNO2 only)                               | Baseline                | n/a    |
| Continuous | AGE                   | Age  | Baseline                | n/a    |

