### 2.5.1 The PRO2TECT studies (CI-0014 and CI-0015)

The primary safety analysis will be based upon all first events that accrue over the two PRO2TECT trials. If the noninferiority (NI) margin is 1.25 and the event rate is the same in the two treatment groups (i.e., the hazard ratio (HR) is 1.0), then 631 events are needed to establish NI with 80% power; 631 events yields more than 90% power to exclude an NI margin of 1.30. If the HR is 0.95 favoring vadadustat, the power is above 90% when the NI margin is 1.25.

Justification for the NI margin of 1.25 for FDA decision making and 1.30 for EMA decision making is provided in [Appendix C](#).

An annual MACE rate of 10% is anticipated. This rate is based on a comprehensive review of available epidemiology and prospective clinical studies in NDD-CKD. Therefore, a projected total of 3700 subjects will be enrolled in studies CI-0014 and CI-0015. With 1850 subjects planned per treatment group in studies CI-0014 and CI-0015 and a planned accrual period of approximately 20 months, and up to 36 months of follow-up (with expected mean follow-up about 2 years), the number of MACE in each study will be a function of the actual pattern and size of enrollment as well as the duration of follow-up.

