**Competing Risk**

```
proc phreg data=&INDAT.;  
  class study TRT(ref="DARB") STRAT2_HF STRAT3_REG AGE SEX  
    RACE HX_CV_ALL HX_DM;  
  strata study;  
  model T*Status(0)= HB_base STRAT2_HF STRAT3_REG TRT AGE SEX RACE  
HX_CV_ALL HX_DM / eventcode=1 ties=Efron rl;  
  Ods ouput ParameterEstimates = HR_EST;  
Run;
```

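### The primary MACE model splits age at 65, on a boundary that differs from the subgroup cut, although age in years is available; the effect is a slight pull of the hazard ratio towards 1

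*SAP*

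**What the plan says.** **Model.** MACE SAP section 4.4 fits a Cox model stratified by study to the CI-0014/CI-0015 pair. Its covariates include "sex (male; female), age", with age split into over 65 and 65 or under. Baseline Hb is in the same list with no categories. The upper confidence limit from this model is compared with 1.25 (FDA) and 1.30 (EMA).

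**Code.** The short code in section 4.4 names age without a coding: "covariates*/ age sex race pre-existing". It points to Appendix A for details, but Appendix A holds only competing-risk and restricted-mean code. The competing-risk model, which section 4.6 gives the same covariates as the primary model, declares AGE as a class variable and leaves baseline Hb out of that statement: "class study TRT(ref='DARB') STRAT2_HF STRAT3_REG AGE SEX".

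**Subgroups.** MACE SAP section 5.1 uses under 65 and 65 or over, as does section 11 of the main SAP.

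**Availability.** The imputation-model table in the main SAP (Table B 1) types the variable as "Continuous | AGE". The by-subject adverse event listing in main SAP section 10.3 includes "center, subject identifier, age, sex, race".

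The SAPs give no reason for the split and plan no sensitivity analysis with continuous age.

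**The concern.** With two bands, a subject of 40 and one of 64 get the same modelled risk, as do subjects of 66 and 90. MACE includes death from any cause, and the plan itself chose age as an adjustment variable, so it is fair to ask why the variable is not used in full. Risk variation left inside the bands acts as an omitted covariate. In a Cox model this pulls the treatment hazard ratio towards 1. In a superiority test that would be conservative; in a noninferiority test it helps the new drug.

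The boundary is also inconsistent. A subject aged exactly 65 is in the younger category in the model and in the older subgroup.

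Finally, the text and the two code fragments agree only if AGE has already been recoded to two levels. Run on age in years, the section 4.4 code would fit a linear term and the Appendix A code would fit one level per distinct age.

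**Working it through.** **Step 1: the plan's own figure.** Main SAP section 2.8 sizes the trial "based on a 2-sided 95% confidence interval for the hazard ratio (HR"). MACE SAP section 2.5.1 states: "If the noninferiority (NI) margin is 1.25 and the event rate is the same in the two treatment groups", "then 631 events are needed to establish NI with 80% power". With 1:1 allocation the Schoenfeld formula is

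events = 4 (z0.975 + z0.80)² / (ln 1.25)² = 4 (1.960 + 0.842)² / 0.2231² = 31.40 / 0.0498 = 630.5, that is 631.

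The standard error of the log hazard ratio is √(4/631) = 0.0796. Power is 80.0% at margin 1.25, 90.9% at margin 1.30, and 93.1% at margin 1.25 with a true hazard ratio of 0.95. All the stated figures reproduce. The formula has no covariate term, so the coding of age cannot change 631.

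**Step 2: inputs for the comparison.** From MACE SAP sections 2.2 and 2.5.1: 3700 subjects, 1:1 allocation, 20 months of accrual, a 10% annual rate (hazard −ln 0.90 = 0.105), and a stop at 631 events. Assumed, because the documents are silent: age Normal with mean 66 and SD 13, clipped to 18–95; a log-linear age effect with hazard ratio 1.3, 1.5 or 1.8 per 10 years; no dropout. Each simulated trial was analysed twice by a Cox model with treatment and age, first with age as over 65 and then as continuous. There were 5000 trials per scenario.

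**Step 3: information kept.** The squared correlation between age and the over-65 indicator is 0.643, so about 36% of the variance in age is discarded.

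**Step 4: true hazard ratio 1.0.** Entries are two-band / continuous.

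| Age HR per 10 y | Model SE | Empirical SD | Power, margin 1.25 | Trials with different verdicts |
|---|---|---|---|---|
| 1.3 | 0.0797 / 0.0797 | 0.0790 / 0.0789 | 80.4% / 80.7% | 2.1% |
| 1.5 | 0.0797 / 0.0797 | 0.0778 / 0.0781 | 81.3% / 81.0% | 3.0% |
| 1.8 | 0.0797 / 0.0797 | 0.0792 / 0.0792 | 79.7% / 79.8% | 5.0% |

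Precision and power do not differ. The two log hazard ratios from one trial differ with SD 0.0076, 0.0126 and 0.0194, which is 10%, 16% and 24% of the SE of 0.0797. That difference goes either way.

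**Step 5: true age-conditional hazard ratio 1.25.** Entries are two-band / continuous.

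| Age HR per 10 y | Mean estimated HR | False noninferiority (nominal 2.5%) |
|---|---|---|
| 1.3 | 1.249 / 1.250 | 2.6% / 2.5% |
| 1.5 | 1.247 / 1.250 | 2.9% / 2.6% |
| 1.8 | 1.241 / 1.250 | 3.3% / 2.7% |

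A separate run of 1500 trials per scenario gave means of 1.252, 1.249 and 1.242 with two bands, against 1.254, 1.252 and 1.251 with continuous age. The pull towards 1 is therefore reproducible.

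The error-rate gap is less firm. In the 5000-trial run the two codings gave different verdicts in 0.42%, 0.70% and 1.50% of trials at this hazard ratio. The standard error of the paired gap is about √(discordance/5000) = 0.09, 0.12 and 0.17 percentage points, against gaps of 0.10, 0.30 and 0.62 points. The gap is within noise at the weakest age effect and outside it at the strongest. With 1500 trials the standard error of a single 2.5% rate is √(0.025 × 0.975/1500) = 0.40 points, so a continuous-age rate as high as 3.2% is compatible with the nominal level. Allowing for run-to-run variation, the rates are about 2.5–3.3% for two bands and 2.5–3.2% for continuous age.

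**The case against.** The strongest reply is that this is a valid prespecified model and that changing it gains almost nothing. Much of that stands.

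- **Power and precision.** A reader might infer that the split wastes power, inflates the variance of the treatment effect or undermines the 631 events. Steps 1 and 4 show that it does none of these.
- **Chance imbalance.** A reader might infer that age imbalance within the bands biases the result. Under randomisation that imbalance is already covered by the confidence interval. At a true hazard ratio of 1 it moves the estimate in either direction.
- **Estimand.** A hazard ratio adjusted less fully for age is a slightly different quantity, and the SAP does not define 1.25 or 1.30 as conditional on exact age. Its margin appendix draws on earlier trials' hazard ratios with no stated age adjustment. This is fair, and it means that attenuation here is relative to the age-conditional hazard ratio. But the plan already chose to condition on age. How fully to do so should be deliberate, and the coarser choice leans towards noninferiority.
- **Other covariates.** The simulation contains only treatment and age. The planned model also adjusts for cardiovascular history, diabetes, NYHA class, sex, race, region and Hb, so the incremental effect in the full model is untested.
- **Functional form.** A linear term assumes log-linearity, and a simulation built on a log-linear effect favours it. This is a real, small downside.
- **The cut mismatch.** Section 5 calls the subgroup analyses exploratory, and section 5.1 drops a covariate from the model when it defines the subgroup. The two boundaries never meet in one model, and only subjects aged exactly 65 change label. This is a matter of consistency and changes no inference.
- **Imputation model.** Continuous age in the haemoglobin imputation model does not contradict the MACE model. It shows only that the variable is available.

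**Conclusion.** The point holds and is minor. The primary MACE model uses age more coarsely than the data allow, on a boundary that disagrees with the subgroup cut. It leaves residual heterogeneity that slightly attenuates the hazard ratio in the direction that favours noninferiority. Under assumed age hazard ratios of 1.3 to 1.8 per 10 years, a true 1.25 is estimated at about 1.24–1.25. The false-noninferiority rate is about 2.5–3.3%, against 2.5–3.2% with continuous age, and the two codings reach different verdicts in 2–5% of trials when the true hazard ratio is 1. These sizes depend on an age distribution and an age effect that the documents do not give. The documents do not support reading this as an underpowered analysis, an inefficient one, or an error in the event count.

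**What to change.** Make these changes before database lock and unblinding:

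1. In MACE SAP section 4.4, enter age in years as a continuous covariate. Use a linear term, or a spline with knots fixed in advance if log-linearity is doubted.
2. In MACE SAP Appendix A, remove AGE from the CLASS statement and add the full primary Cox code. Changes 1 and 2 must go together, because age in years left as a class variable would be fitted as one level per distinct age.
3. Use one cut, under 65 and 65 or over, wherever age categories are needed.

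The cost is a few lines of text and code and no new data. The only statistical price is the functional-form assumption for age.
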